6.7. Treatment Characteristics

ICM procedure characteristics and exposure to study product will be collected on eCRF for all attempted insertions. Procedure characteristics to be summarized may include, but are not limited to: referring physician type, procedure clinician type, procedure location type, reason for ICM insertion, procedure time, anesthesia usage, insertion tools, monitor suturing, wound closure method, infection control methods, monitor position/orientation.

For continuous variables, mean, standard deviation, median, and range will be reported. For categorical variables, frequency and percentage will be reported.

6.8. Interim Analyses

Abstracts, posters and presentations are expected based on this dataset throughout the study. No type I error correction or alpha spending will be performed for analyses conducted in support of publications occurring while the study is ongoing.

6.9. Evaluation of Objectives

Primary Objective #1

Characterize clinical actions initiated by Reveal LINQ arrhythmia detection.

i. Analysis Methods

This objective is descriptive in nature. New onset of arrhythmias diagnosed as results of ICM data review, and the subsequent clinical actions taken are reported through CRFs.

Study sites will review device recorded arrhythmia episodes via remote transmission or at a regularly scheduled clinic visit. Clinical treatments may be prescribed upon diagnosis.

Summary statistics will be obtained for frequencies of diagnosis and treatment. Frequencies of each action taken, such as medication changes, surgical intervention, new cardiac device implant, etc. will be obtained.

Endpoint definition: First incidence of onset of new arrhythmias for each type diagnosed as result of ICM data review during the study, regardless of whether or not the patient had arrhythmias also reported in their medical history. The subsequent clinical actions taken are reported through Follow-up CRFs.

Follow-up CRF question 9) "Were any new diagnoses made as a result of review of ICM data during this visit" where arrhythmia type is selected, considering only the *first* diagnosis of each type for the subject and linking to Treatment log "Treatment Type" with Treatment Trigger checked as being "Monitor Data" and where treatment date is on or after first diagnosis of event.

Example output shell:

Arrhythmia type	Number of patients (%)
Atrial Fibrillation	N (%)
Bradycardia	N (%)
Tachycardia	N (%)
Overall total	N (%)

Atrial Fibrillation	N (%)									
Bradycardia	N (%)									
Tachycardia	N (%)									
Overall total	N (%)									

Additional analysis

An additional sensitivity analysis will be performed to account for the follow-up time of subjects in study and characterize the incidence of first arrhythmias and actions taken by arrhythmia type. This sensitivity analysis will be done to account for potential differences in reporting for those subjects enrolled after insertion who may not have fully reported actions taken between insertion and consent.

ii. Determination of Subjects/Data for Analysis

Any enrolled subjects who are diagnosed with an arrhythmia detected by Reveal LINQ will be included in analysis.

iii. Sample Size

There is no statistical hypothesis formulated for this analysis therefore there is no sample size for this objective.

Primary Objective #2

Estimate procedure-related acute infection rate (up to 30 days post insertion procedure).

i. Analysis Methods

The postinsertion procedure visit can be either in office visit or CareLink visit. Infection events will be reported by study sites upon awareness. The acute infection rate will be calculated by dividing the number of subjects with infection events within 30 days post insertion procedure by the number of subjects in the risk set (the analysis cohort). Two-sided 95% confidence interval will be calculated using the Exact Binomial method. Additionally, rate for infection SAE may be calculated (see CIP v2 Appendix for SAE definition).

Also, since infection rates may be quite small, a sensitivity analysis will be performed using the Wilson Interval.

Endpoint definition: The numerator will be number of subjects with Infection (Question 4 “Classify the event/primary diagnosis” on Event CRF is marked as “Infection”) where days to event onset is less than or equal to 30 day post-insertion. Denominator as per Determination of Subjects/Data for Analysis below.

Infection is considered serious if any of the questions under the “Seriousness: Did the adverse event meet any of the following criteria” header on the event CRF are answered as “Yes”

Example SAS code:

```
PROC FREQ data=events;
  TABLE InfectionAcute / alpha=0.05 binomial (exact);
RUN;

PROC FREQ data=events;
  TABLE InfectionAcute / alpha=0.05 binomial (Wilson);
RUN;
```

[figure not shown]
[figure not shown]
[figure not shown]
ii. Determination of Subjects/Data for Analysis

[figure not shown]
[figure not shown]
A subject will be included in the analysis cohort for this objective as long as the subject was enrolled in the study prior to implant and one of the following criteria is met:

- a) A subject who undergoes a Reveal LINQ insertion procedure and completes a minimum of one visit at a time point ≥ 30 days post insertion procedure will be included for the analysis.
- b) A subject will be included in the analysis if an infection event is reported regardless if the subject has completed 30 day follow-up.
- c) A subject with a Reveal LINQ device explanted after a successful implant procedure that occurred prior to 30 days post insertion procedure will be included in the analysis cohort.
- d) A subject who undergoes a Reveal LINQ implant procedure without having a Reveal LINQ device chronically implanted will be included in the analysis with a confirmation of patient status at ≥ 30 days post implant.

[figure not shown]
Ancillary Objectives

[REDACTED]	[REDACTED]
[REDACTED]	
[REDACTED]	[REDACTED]

[REDACTED]
[REDACTED]

[figure not shown]
[REDACTED]

[REDACTED]
[REDACTED]

[REDACTED]
[REDACTED]

[REDACTED]

[REDACTED]	[REDACTED]

A large black rectangular redaction box covers the majority of the page content, starting below the header and ending above the footer. The redaction is irregular, with some white space visible at the top and bottom edges. The rest of the page is white with no other content.

[REDACTED]

[REDACTED]	[REDACTED]	[REDACTED]

[REDACTED]

[REDACTED]	[REDACTED]

[REDACTED]	[REDACTED]

[REDACTED]	[REDACTED]

[REDACTED]
[REDACTED]

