7.9 Subject Follow-up

All subjects are followed in-office in accordance with the standard care practices of their respective care provider. However, in addition to the scheduled follow up visits, real time reporting is required for arrhythmia events and actions taken. Follow-up data collection is required at minimum every 6 months (+/- 3 months) post-insertion as shown in Figure 1.

The following information will be collected within the follow-up windows shown in Figure 1:

- Subject Arrhythmia/Symptom Status
- Treatments
 - Assess subject status and/or review subjects medical records for occurrence of any of the following treatments and indicate whether they were triggered by the Reveal LINQ ICM data review or any other reason:
 - AF ablation
 - Cardioversion (electrical and/or pharmacological)
 - Implant of cardiac rhythm system

- Medication changed/administered
- Revascularization (PCI and/or CABG)
- Or other cardiac treatment
- Device/Monitor Data
 - New Diagnoses as a result of Reveal LINQ ICM data
 - Actions taken as a result of monitor data review
 - Submit complete device data via device transmission (i.e., CareLink), or transfer from a printout to the eCRF
- Medications (if the subject received an AF Ablation since Reveal LINQ ICM implant)
- Imaging testing results
 - Medtronic requests that the site send any copies of these test results completed as part of standard of care by the time the subject is exited from the study
- Adverse Events Assessment

7.9.1 *Follow-up Due to AF Ablation*

Subject follow-up may also include:

- Ablation Procedure
 - Collected for each ablation procedure that occurs post Reveal LINQ ICM insertion
 - Payer information
 - Heart Rhythm Status
 - Procedure Information
 - Ablation Strategy
 - Device Information
 - Imaging/Navigation
 - Procedure Results
 - Discharge
 - Adverse Event Assessment
- AF follow-up
 - If an AF ablation(s) occurred after Reveal LINQ ICM insertion, AF follow-up information is collected at all follow-up visits
 - Recurrent atrial arrhythmias
 - AF ablation related adverse event assessment and description
- AF Status
 - If an AF ablation(s) occurred after Reveal LINQ ICM insertion, AF status is collected at follow-up visits in which the subject experienced recurrent atrial fibrillation since the previous follow-up
 - AF Status details
 - Cardiac Medications History

7.9.2 *Modes of Data Collection*

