7.9.4 Arrhythmia Event and Action Taken Assessment (ongoing)

Data may be collected more than once within each designated follow-up window as real time reporting is required for Arrhythmia Events and Actions Taken.

- Arrhythmia Event
 - Regardless if action is taken, any time a new arrhythmia is recorded on the device a follow-up form is required
- Action Taken
 - If an action is taken as a result of an arrhythmia, a follow-up form is required. Actions include:
 - Medication change
 - Treatment
 - AF ablation
 - Cardioversion (electrical and/or pharmacological)
 - Implant of cardiac rhythm system
 - Medication changed/administered
 - Revascularization (PCI and/or CABG)
 - Or other cardiac treatment
 - Diagnostic work up
 - CT/MRI/PET Scan, X-Ray/Fluoroscopy, Cardiac Catheterization, Biopsy, Echocardiogram, Exercise Stress Test, Venous Ultrasound,

Radionuclide ventricular angiography/MUGA, Tilt test, electroencephalography (EEG), Electromyography (EMG), Laboratory test, Doppler of carotids/intracerebral arteries and other

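### SAP 6.9 derives Objective 1 clinical actions only from the Treatment log and names no source for the diagnostic work-ups that the protocol lists as actions

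*SAP*

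**What the plan says.** **The objective.** SAP 6.9 states Primary Objective #1 as: "Characterize clinical actions initiated by Reveal LINQ arrhythmia detection". It is descriptive: "There is no statistical hypothesis formulated for this analysis therefore there is no sample size for this objective".

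**What counts as an action.** Protocol 7.9.4 says: "If an action is taken as a result of an arrhythmia, a follow-up form is required. Actions include". It then gives three groups: medication change, treatment, and "Diagnostic work up". The third group has its own list of tests, beginning "CT/MRI/PET Scan, X-Ray/Fluoroscopy, Cardiac Catheterization, Biopsy, Echocardiogram, Exercise Stress Test, Venous Ultrasound" and going on to tilt testing, EEG, laboratory tests and others.

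**What is collected at follow-up.** Protocol 7.9 has a Treatments item that records what triggered each treatment. It covers ablation, cardioversion, rhythm-device implant, drug changes, revascularization and a catch-all for other cardiac treatment. It names no diagnostic test. Under a different heading, Device/Monitor Data, the same section collects "Actions taken as a result of monitor data review".

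**How the SAP derives actions.** The endpoint definition in SAP 6.9 takes the first diagnosis of each arrhythmia type from question 9 of the Follow-up CRF. It then finds the action by "linking to Treatment log 'Treatment Type' with Treatment Trigger checked as being 'Monitor Data", with the treatment dated on or after that diagnosis. No other field is named as a source of actions.

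**What the SAP says more generally.** The same section undertakes to give frequencies for each action, with an open-ended list of examples, and says that actions are reported on the Follow-up CRFs.

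**Declared changes.** SAP 6.12 lists two changes from the protocol for this objective: counting only the first incidence, and a sensitivity analysis for follow-up time.

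**The concern.** The objective concerns actions, but the rule a programmer would follow retrieves treatments. The protocol keeps the two apart: it lists work-ups separately from treatments, and it collects an actions item separately from the Treatments item.

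If the primary table is built from the Treatment log alone, a whole class of response to a detection may be missing from a result headed clinical actions. An example is a subject whose detection led to an echocardiogram and a catheterization but to no change in drugs or devices. That subject would have no linked action under the rule as written.

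The registry's stated purpose includes locating the device in the care pathway, and further testing is part of that pathway. SAP 6.8 expects abstracts and presentations while the study is running, so an undeclared treatment-only definition could be published under the wider label.

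**Working it through.** Objective 1 has no sample size, expected rate or other planned figure to reproduce. The check is therefore a comparison of texts, following each protocol action group to the SAP rule.

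| Action group (Protocol 7.9.4) | In the Treatments list of Protocol 7.9? | Route into the SAP 6.9 rule |
|---|---|---|
| Medication change | Yes, as a drug change or administration | Treatment log, trigger Monitor Data |
| Treatment | Yes | Treatment log, trigger Monitor Data |
| Diagnostic work-up | No | None named |

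**Step 1. Could work-ups enter through the Treatment log?** Only if the Treatment Type options include tests. The option list is not in the documents, because Protocol Appendix A supplies the draft forms separately. The treatment list in Protocol 7.9 suggests that they do not, and a catch-all for other cardiac treatment is not a natural home for an EEG or a laboratory test. The point remains conditional on the form.

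**Step 2. Could they enter through the actions item?** It would be the obvious source, since Protocol 7.9.4 says: "If an action is taken as a result of an arrhythmia, a follow-up form is required". The SAP derivation does not refer to it.

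**Step 3. Could they enter through the imaging files?** No. SAP 6.13 says that images sent by sites and stored device data will not be used for statistical analysis of the objectives.

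**Step 4. Is the restriction declared?** Neither Objective 1 entry in SAP 6.12 mentions it.

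**Step 5. Direction and size.** Consider any summary that counts subjects with at least one linked action. Let *A* be the share of diagnosed subjects with any action in the protocol's sense. Let *s* be the share of those whose only action was a work-up. If work-ups have no route, the rule returns

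*A* × (1 − *s*), a shortfall of *A* × *s*.

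The shortfall cannot be negative, and it is zero if no subject has a work-up as the only action. The documents give neither *A* nor *s*. To show the arithmetic only, assume *A* = 60%:

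- *s* = 5%: 60% × 0.95 = 57%, a shortfall of 3 points
- *s* = 15%: 60% × 0.85 = 51%, a shortfall of 9 points
- *s* = 30%: 60% × 0.70 = 42%, a shortfall of 18 points

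These are assumed inputs, not estimates for this registry. The frequency table by action type is affected differently: the treatment counts are unchanged, and the work-up category has no entries.

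**The case against.** The strongest reply is that the plan is incompletely specified and does not actually exclude work-ups. Several parts of that reply stand.

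- **Protocol 12.1 leans towards treatment.** The protocol's own analysis section plans frequencies of diagnosis and treatment, and its named examples are drug changes, surgery and device implants. SAP 6.9 follows it closely. Section 7.9.4 says when a form is due; it does not define the endpoint. This weakens any charge that the SAP departs clearly from the protocol's analysis plan. It does not remove the conflict inside SAP 6.9, which promises every action and then specifies a rule that reaches only the Treatment log.
- **Key material is unseen.** The Treatment Type options are on forms not included here, and the column headings of the second output table were lost in reading the PDF. A reader might infer that subjects with only a work-up will be shown as having no action. The documents do not support that: no such category is visible anywhere in the SAP.
- **Work-ups may be reported elsewhere.** The protocol synopsis lists ancillary objectives on healthcare utilization and on conditions diagnosed and actions taken. Their SAP methods are redacted. A reader therefore cannot conclude that the registry will fail to report work-ups. Ancillary reporting would still not complete a primary result worded as clinical actions.
- **The readable text does not plan an any-action proportion.** It plans frequencies by type. The formula above therefore applies only if such a summary is produced.

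**Conclusion.** The point holds in a limited form. SAP 6.9 gives one derivation for Objective 1 actions, and it names no source for diagnostic work-ups, which the protocol lists as actions. Applied literally, it leaves them out of the primary result, contrary to the section's own promise and without a declaration in 6.12.

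This rests on one assumption: that the Treatment Type options do not include tests. The protocol's treatment list makes that likely but does not prove it.

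The size cannot be determined from the documents. A reader might be tempted to attach a figure in percentage points to the understatement, but any such figure only returns the share of work-up-only subjects that was assumed. What can be said is the direction: omitting an action class can lower a count of subjects with any action, and cannot raise it.

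**What to change.** In SAP 6.9, take Objective 1 actions from two sources: the Treatment log with trigger Monitor Data, and the follow-up form's item on actions resulting from monitor data review. Remove duplicates where one action appears in both. Report diagnostic work-up as its own category alongside treatments. State how a work-up is tied to a first diagnosis, since the present date condition is written for treatments.

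If the sponsor intends treatments only, label the result as treatments and add the restriction to the Objective 1 entries in 6.12. If the Treatment Type options already include tests, one sentence in 6.9 saying so would settle this point.

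The cost is SAP wording and modest programming. The protocol indicates that the data are already collected, although the form should be checked to confirm that the actions item identifies work-ups. The main burden is de-duplication across the two sources.

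### SAP 6.9 links treatments to arrhythmia types by trigger and date only, so in subjects with several types one action can be credited to types that did not prompt it

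*SAP*

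**What the plan says.** The objective in SAP 6.9 is to "Characterize clinical actions initiated by Reveal LINQ arrhythmia detection". The endpoint definition takes new diagnoses from the Follow-up CRF, "considering only the *first* diagnosis of each type for the subject", so one subject can stand in several arrhythmia rows.

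Each first diagnosis is then linked to the Treatment log on two conditions:

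- the entry is one "with Treatment Trigger checked as being" monitor data;
- it qualifies "where treatment date is on or after first diagnosis of event".

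No condition on arrhythmia type, form or visit is stated. There is no upper time limit and no rule for subjects with several types. The rows of the output shells are arrhythmia types. The follow-up-time sensitivity analysis is also meant to "characterize the incidence of first arrhythmias and actions taken by arrhythmia type".

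Protocol 7.9 has sites list treatments and "indicate whether they were triggered by the Reveal LINQ ICM data review or any other reason". Protocol 7.9.4 says that "any time a new arrhythmia is recorded on the device a follow-up form is required", and also: "If an action is taken as a result of an arrhythmia, a follow-up form is required".

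**The concern.** The trigger field, as Protocol 7.9 describes it, separates device data from everything else. It does not say which arrhythmia prompted the treatment, so the date condition alone sorts treatments into type rows. Suppose bradycardia is first diagnosed on day 60 and AF on day 200, and medication is changed for AF on day 205. The change satisfies both conditions for both types and appears in both rows.

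A reader will take each row as the actions that arrhythmia set off. If the row also holds actions prompted by another arrhythmia, it overstates them. It does so most for the type that is itself less often treated, and this makes action rates look more alike across types than they are. A larger sample does not remove the effect. SAP 6.8 expects abstracts and presentations during the study, so the rows may circulate early.

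**Working it through.** **1. The rule applied literally.** Made-up subject: AF first diagnosed 10 January, bradycardia 1 March, tachycardia 1 September.

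- Monitor-triggered device implant on 5 March: linked to AF and bradycardia.
- Monitor-triggered AF ablation on 1 October: linked to AF, bradycardia and tachycardia.
- Treatment with any other trigger: linked to none.

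**2. Does other text repair it?** Protocol 12.1 gives no linking rule. SAP 6.12 lists two items for this objective, first incidence and follow-up time; neither concerns attribution by type. The sensitivity analysis addresses late enrolment, and no different link is stated for it.

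**3. Size if each action answers one arrhythmia.** The plan has no figure to reproduce, since the objective has no hypothesis and no sample size. Every input below is assumed except the 3-year follow-up: independent exponential times to first AF and first bradycardia, type-specific probabilities of action, and a mean delay to action of 0.1 year. An approximate formula for the inflation of a row is

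P(other type | this type) × other type's action rate × 0.5 × (1 − own action rate), with P(other type) = 1 − exp(−3 × its yearly rate).

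The 0.5 is roughly the chance that this type was diagnosed first. The last factor is there because a subject already counted in the row cannot be counted again. For the less-treated row (bradycardia):

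- Case A (0.02/yr each; 60% and 50% acted on): 0.058 × 0.60 × 0.5 × 0.50 = 0.9 points
- Case B (AF 0.05, bradycardia 0.02/yr; 60% and 30%): 0.139 × 0.60 × 0.5 × 0.70 = 2.9 points
- S1 (0.10 and 0.05/yr; 60% and 30%): 0.259 × 0.60 × 0.5 × 0.70 = 5.4 points
- S2 (0.15 and 0.10/yr; 60% and 10%): 0.362 × 0.60 × 0.5 × 0.90 = 9.8 points

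Simulation of 4 million subjects per case:

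| Case | Diagnosed subjects with both types | True row | SAP rule | Excess (points) |
|---|---|---|---|---|
| A | 3.0% | 48.3% | 49.2% | 0.9 |
| B | 4.3% | 28.9% | 31.8% | 2.9 |
| S1 | 10.0% | 29.1% | 34.5% | 5.4 |
| S2 | 17.8% | 9.7% | 19.3% | 9.6 |

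The more-treated row rises by 0.3 to 1.5 points. The overall row, counted once per subject, does not change (51.2% in S1 and 43.9% in S2, true and SAP rule alike). In single-type subjects the SAP rule equals the truth. With one later repeat action per treated type (mean gap 1 year), the excess is 1.1 (A), 6.8 (S1) and 12.4 (S2) points.

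**4. Size if some actions answer both types.** Let half of the actions taken when both types are already known answer both (assumed). The last column assigns each treatment to the most recent preceding first diagnosis instead.

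| Case | True row | SAP rule | Most recent diagnosis |
|---|---|---|---|
| S1 | 31.9% | 34.6% (+2.7) | 29.3% (−2.6) |
| S2 | 14.5% | 19.4% (+4.9) | 10.2% (−4.3) |

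At a 75% share the SAP rule is clearly closer (S1: 33.1% true, 34.4% SAP, 29.2% alternative; S2: 17.0%, 19.4%, 10.3%). At 25% the alternative is closer.

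**5. A single action cell.** The SAP wants the frequency of each action, not only of any action. Suppose no implant is truly given for AF. Let o be the share of AF subjects who also have bradycardia, p the share of these implanted for bradycardia, and q the share of those with AF diagnosed on or before the implant. The AF row then shows 100 × o × p × q. With assumed ranges this runs from 100 × 0.10 × 0.30 × 0.50 = 1.5% to 100 × 0.40 × 0.60 × 1.00 = 24%.

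**The case against.** The endpoint can be read as purely temporal: a first diagnosis, then whatever actions follow. On that reading the objective asks for attribution to the device, which the monitor-data trigger supplies, and overlapping rows are a legitimate descriptive convention. The SAP also says that it sets out only minimal requirements. The CRFs are not supplied (Protocol Appendix A), so a log entry may carry a type, reason or visit key. The column headings of the second shell are lost in extraction. And where one treatment does answer two arrhythmias, crediting both is correct.

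Much of this stands. An inclusive count is defensible if it is labelled as one, but nothing visible labels it so, and the rows are presented by arrhythmia under an objective about actions initiated by detection. A key may exist on the CRF, but the stated rule does not use one. A reader might infer that the data cannot support attribution by type. The documents do not show that: Protocol 7.9.4 ties the follow-up form both to new arrhythmias and to actions taken, so a form-level link is plausible.

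The objection is strongest on the remedy. A reader might infer that assigning each treatment to the most recent diagnosis should become the primary rule. Its advantage depends on how often one action answers two arrhythmias, which the documents do not say. It can also do worse in the more-treated row: in S2 with a 0.5-year mean delay the AF row is 51.5% in truth, 52.0% under the SAP rule and 49.8% under that assignment.

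**Conclusion.** The mechanism follows from the rule as written. In subjects with two or more types, a type row can include actions that type did not initiate. The direction is upward, mainly in the less-treated row.

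The size is not known. Figures of about 1 to 10 points (up to 12.4 with a repeat action) assume that each action answers one arrhythmia, and every rate behind them is assumed. They are neither bounds nor estimates for this registry, and the upper end needs high rates and a wide gap in action rates between types. With half of the actions shared, the excess is about 3 points in S1 and 5 in S2.

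A reader might also infer that the overall total is inflated. It is not if each subject is counted once, though the SAP does not say how that row is formed. The objective is descriptive, so no test or error rate is affected; what is affected is how a primary result by type is read. That makes the point worth fixing. Confidence is medium, because the CRFs and part of the shell are not visible.

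**What to change.** In SAP 6.9:

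1. Where the CRF holds a type or reason field, or the treatment is reported on the same follow-up form as a new diagnosis, credit the treatment to that type or types; more than one is allowed.
2. Where no such link exists, keep the current date rule, label those rows as any later monitor-triggered action, and footnote that type rows overlap. Report how many treatments were credited to more than one type.
3. Add the action-by-type table restricted to subjects with a single diagnosed type.
4. Add assignment to the most recent preceding first diagnosis as a sensitivity analysis only, and show it beside the date rule as a range.
5. State that the overall row counts each subject once.

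The cost is SAP wording and some linkage programming, with no new data collection if a form or field link exists. The same-form link has not been tested numerically; later treatments reported on a form without a new diagnosis will fall under item 2. The single-type table is a selected subset, so it supports the main rows but cannot replace them. The most-recent-diagnosis assignment undercounts when one action answers two arrhythmias, which is why neither approach should be shown alone.
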